BMI body mass index BSTK bedside sensory testing kit C _{max} maximum observed concentration CI confidence interval CPAP clinical pharmacology analysis plan
BSTK bedside sensory testing kit C _{max} maximum observed concentration CI confidence interval CPAP clinical pharmacology analysis plan
C _{max} maximum observed concentration CI confidence interval CPAP clinical pharmacology analysis plan
CI confidence interval CPAP clinical pharmacology analysis plan
CRF case report form
CRO contract research organization
CRU clinical research unit
CSR clinical study report
C-SSRS Columbia Suicide Severity Rating Scale
CTCAE Common Terminology Criteria for Adverse Events
DDI drug-drug interaction
DSIS Daily Sleep Interference Scale
ECG electrocardiogram
EDC electronic data capture
ETT Early Termination of Treatment
FAS Full Analysis Set
FDA Food and Drug Administration
FSH follicle-stimulating hormone
GCP Good Clinical Practice
GPS Global Patient Safety
HBsAg hepatitis B surface antigen
HCV hepatitis C virus
HIPAA Health Insurance Portability and Accountability Act
HIV human immunodeficiency virus
ICF informed consent form
ICH International Council for Harmonization
IEC independent ethics committee
IRB institutional review board
IXRS interactive response system in which X represents voice or web, such as IWRS
max maximum value
MedDRA Medical Dictionary for Regulatory Activities
min minimum value
MMRM mixed-effects model for repeated measures
MRC Medical Research Council
n number of subjects

[figure not shown]
Abbreviation	Definition
Na _v	voltage-gated sodium channels
NCS	nerve conduction studies
NRS	numeric rating scale
PCS	potentially clinically significant
PD	pharmacodynamic, pharmacodynamics
PE	physical examination
PGIC	patient global impression of change
PK	pharmacokinetic, pharmacokinetics
PR	PR interval, segment
prn	as needed
qd	daily
QRS	the portion of an ECG comprising the Q, R, and S waves, together representing ventricular depolarization
QT	QT interval
QTc	QT interval corrected
QTcF	QT interval corrected by Fridericia's formula
SAE	serious adverse event
SAP	statistical analysis plan
SD	standard deviation
SE	standard error
SET	study execution team
SGOT	serum glutamic oxaloacetic transaminase
SGPT	serum glutamic pyruvic transaminase
SI	SI units (International System of Units)
TEAE	treatment-emergent adverse event
US	United States
WHO-DDE	World Health Organization-Drug Dictionary Enhanced

5 INTRODUCTION

Pain is the most common symptom for which patients seek medical attention. It is a protective mechanism designed to prevent tissue injury. When pain persists beyond its usefulness, it becomes pathological and can prove debilitating. Current pain therapies suffer from poor efficacy and have a high risk of adverse events (AEs). For example, lidocaine (a nonselective sodium channel blocker) may effectively reduce pain, but its utility is limited because of prominent side effects when given at dose levels required for pain relief. Opioid pain medications have a high abuse liability with approximately 16,000 annual deaths in the US and between 10,000 and 20,000 annual deaths in Europe due to overdose. In addition, opioid-induced hyperalgesia also limits the long-term use of opioids. While the incidence of opioid-induced hyperalgesia is not known, it is encountered regularly in clinical practice and creates significant challenges in pain management. The limited treatment options for pain, particularly chronic pain indications, combined with a growing awareness of the risks of the current standards of care underscore the need for new pain management therapies.

Voltage-gated sodium channels (Na_v) play a critical role in pain signaling based on both nonclinical and clinical evidence. Evaluation of the role these channels play in normal physiology and the pathological states arising from mutations in sodium channel genes and animal models, as well as the pharmacology of known sodium channel modulating agents, all point to the critical role of Na_vs in pain sensation.⁵⁻⁷ The Na_v1.8 channel is primarily restricted to peripheral neurons that sense pain (e.g., dorsal root ganglia) and is known to mediate pain sensation and chronic pain. For example, Na_v1.8 gain-of-function mutations are thought to directly cause chronic pain in some patients with painful small fiber neuropathy.⁸⁻¹⁰ This channel has been identified as a target for analgesia¹¹ and selective Na_v1.8 blockers, which have the potential to treat pain indications where the primary mechanism for pain is nociceptor hyperexcitability.

VX-150, an orally bioavailable prodrug that rapidly converts in vivo to the active moiety VRT-1207355, is being developed for the treatment of pain. VRT-1207355 is a Na_v1.8 blocker that is highly selective for Na_v1.8 relative to the other sodium channel subtypes.

One Phase 2a study has completed dosing; Study VX15-150-101 (Study 101) is a proof of concept study to evaluate efficacy in patients with osteoarthritis pain. Overall, VX-150 has been well tolerated without any safety concerns. Additional details of the VX-150 development program are available in the VX-150 Investigator's Brochure. 12

Small fiber neuropathy is a distinct clinical condition caused by diseases affecting peripheral small nerve fibers (Aδ- and C-fibers). Common symptoms include burning pain in the feet and

evoked pain (e.g., pressure and touch allodynia). Diagnosis is defined as possible, probable, and definite based on the combination of symptoms, signs, evidence of large sensory nerve fiber function integrity by nerve conduction studies (NCS) and abnormal skin biopsy or quantitative sensory testing. ^{13, 14} By inhibiting Na_v1.8 in the peripheral nerve fibers, VX-150 has the potential to treat pain caused by hyperexcitability of the damaged or diseased nerves. Study VX16-150-102 is a proof of concept study that will evaluate the efficacy, safety, tolerability, and pharmacokinetics (PK) of VX-150 in the treatment of neuropathic pain in subjects with small fiber neuropathy.

6 STUDY OBJECTIVES

6.1 Primary Objective

To evaluate the efficacy of VX-150 for the treatment of pain caused by small fiber neuropathy

6.2 Secondary Objectives

- To evaluate the safety and tolerability of VX-150
- To evaluate the PK of VRT-1207355 and the metabolite VRT-1268114

[figure not shown]
7 STUDY ENDPOINTS

7.1 Primary Endpoint

Change from baseline in the weekly average of daily pain intensity on the 11-point numeric rating scale (NRS), as reported in the daily diary, at Week 6

7.2 Secondary Endpoints

- Proportion of subjects with ≥30% reduction in the weekly average of daily pain intensity on the 11-point NRS, as reported in the daily diary, at Week 6
- Proportion of subjects with ≥50% reduction in the weekly average of daily pain intensity on the 11-point NRS, as reported in the daily diary, at Week 6
- Change from baseline in the Daily Sleep Interference Scale (DSIS) at Week 6
- Proportion of subjects categorized as improved at Week 6 on the patient global impression of change (PGIC) assessment
- Change from baseline in pain intensity on the 11-point NRS, as reported at study visits, at Week 6
- Plasma PK parameters of VRT-1207355 and the metabolite VRT-1268114
- Safety and tolerability based on the Columbia Suicide Severity Rating Scale (C-SSRS), incidence and type of AEs, changes from baseline in clinically significant laboratory test results, vital signs, and ECGs at each visit

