The neurological component of the Day 1 complete physical examination includes sensory testing conducted with the bedside sensory testing kit (BSTK). Symptom-directed physical examinations will occur at any time during the study if triggered by AEs or if deemed necessary by the investigator.

With the exception of Day 7, PK samples will be collected at any time during the study visit. On Day 7, 2 PK samples will be collected: 1 sample before the dose of study drug, and 1 sample 1 to 4 hours after the dose of study drug.

Table 3-2 Study VX16-150-102: Run-in Period, Treatment Period, and Safety Follow-up Visit

Event/Assessment	Day -7 (During Screening)	Day 1	Day 7 (± 1 Day)	Week 3 (± 3 Days)	Week 6 (± 3 Days)	ETT Visit ^a	Safety Follow-up Visit 28 (± 7) Days After the Last Dose of Study Drug
11-pt numeric rating scale (NRS) pain score via daily diary ⁱ		Day -7 through	n Week 6 or ETT Vi	sit via daily diary			
11-pt NRS pain score at study visits ^j	X	X	X	X	X	X	X
Daily Sleep Interference Scale (DSIS) ^k		Day -7 through	n Week 6 or ETT Vi	sit via daily diary			
Patient global impression of change (PGIC)		X	X	X	X	X	X
Columbia Suicide Severity Rating Scale (C-SSRS)		X	X	X	X	X	X
Study drug count			X	X	X	X	
Medications review		Cont	inuous from signing	of the ICF through	the Safety Follow-up	Visit	·····
Concomitant treatments and procedures		Cont	inuous from signing	of the ICF through	the Safety Follow-up	Visit	
Adverse events		Cont	inuous from signing	of the ICF through	the Safety Follow-up	Visit	

From Day -7 through Week 6 or ETT Visit, subjects will report their average daily pain during the last 24 hours on the NRS each evening. Subjects will also report their current pain immediately before each administration of rescue medication.

At study visits, subjects will report their average pain during the last 24 hours on the NRS.

From Day -7 through Week 6 or ETT Visit, subjects will report each morning on the previous night's sleep using the DSIS.

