9.3 Rationale for Study Design and Study Drug Regimens

9.3.1 Study Design

This study is designed to evaluate the efficacy of VX-150 for treatment of pain in subjects with small fiber neuropathy. The randomized, double-blind study design will limit observer bias, minimize carryover effect and reduce the possibility for unblinding. The potential for a carryover effect is due either to the potential subjective nature of pain measurements and/or the effect of treatment with VX-150. For the primary endpoint, daily NRS pain scores will be averaged over a weekly period to reduce the impact on the analyses of individual high or low pain scores.

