9 STATISTICAL ANALYSIS

9.1 General Considerations

The Schedule of Assessments is provided in Section 3 of CSP. The precision standards for reporting safety and efficacy variables are provided in an internal Biometrics document that specifies the programming rules including the precision for derived variables.

All individual subject data, including those derived, for subjects who were randomized or received at least 1 dose of study drug, i.e. All Subjects Set, will be presented in individual subject data listings as described.

Continuous variables will be summarized using the following descriptive summary statistics: the number of subjects (n), mean, standard deviation (SD), standard error (SE), median, minimum value (min), and maximum value (max).

Categorical variables will be summarized using counts and percentages.

Baseline value for the NRS via daily diary and the DSIS will be defined as the average score of at least 4 nonmissing scores from Day -7 to Day -1. For all other variables baseline will be defined as the most recent nonmissing measurement collected before the initial administration of study drug unless specified otherwise.

Change (absolute change) from baseline will be calculated as post-baseline value – baseline value unless otherwise specified.

Treatment-emergent (TE) Period will be defined as the time from dosing with study drug until the following time point:

- For enrolled subjects who have a Safety Follow-up Visit: through the Safety Follow-up Visit
- For enrolled subjects who do not have a Safety Follow-up Visit, the earliest of
 - 35 days after the last dose of study drug, or
 - the ETT Visit if that visit is 3 weeks or later following the last dose of study drug (see Section 9.1.5 of CSP)

Unscheduled visits: Unscheduled visit measurements will be included in analysis as follows:

- In scheduled visit windows per specified visit windowing rules.
- In the derivation of baseline/last on-treatment measurements.
- In the derivation of maximum/minimum on-treatment values and maximum/minimum change from baseline values for safety analyses.
- In individual subject data listings as appropriate.

Visit windowing rules: The analysis visit windows for protocol-defined visits are provided in [Appendix A](#).

Incomplete/missing data will not be imputed, unless otherwise specified.

Outliers: No formal statistical analyses will be performed to detect or remedy the presence of statistical outliers, unless specified otherwise.

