9.3.2 Analysis of Secondary Efficacy Variables

9.3.2.1 Definition of Secondary Efficacy Variables

Proportion of subjects with $\geq 30\%$, $\geq 50\%$ reduction in the weekly average of daily pain intensity on the 11-point NRS, as reported in the daily diary, at Week 6: The percentage reduction in the weekly average of daily pain intensity will be calculated as following:

$100 \times (\text{daily pain intensity score at baseline} - \text{the weekly average of daily pain intensity score at Week 6}) / \text{daily pain intensity score at baseline}$.

Change from baseline in the DSIS at Week 6: The change from baseline in the DSIS at Week 6 is the change from baseline in the weekly average of daily sleep interference score on the DSIS, as reported in the daily diary at Week 6. The weekly average of DSIS will be calculated by averaging the nonmissing daily sleep interference scores in each week. If the count of nonmissing daily sleep interference scores is less than 4 in a week, the weekly average of daily sleep interference on the DSIS will be set to missing.

Proportion of subjects categorized as improved at Week 6 on the PGIC assessment: The assessment consists of a single item on a 7-point scale from 1 (very much improved) to 7 (very much worse). Subjects will be categorized as following:

- 1 - 2 reported on the PGIC assessment will be categorized as “improved”;
- 3 - 4 reported on the PGIC assessment will be categorized as “no change”;
- 5 - 7 reported on the PGIC assessment will be categorized as “worse”.

Change from baseline in pain intensity on the 11-point NRS, as reported at study visits, at Week 6: Change from baseline in pain intensity will be calculated at each post-baseline visit (Day 7, Week 3 and Week 6) following the general definition of the baseline and change from baseline in Section 9.1.

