9.3.2.2 Secondary Analyses

Proportion of subjects with $\geq 30\%$ reduction in the weekly average of daily pain intensity on the 11-point NRS, as reported in the daily diary, at Week 6: This variable will be evaluated using descriptive statistics by treatment group.

[figure not shown]
Proportion of subjects with $\geq 50\%$ reduction in the weekly average of daily pain intensity on the 11-point NRS, as reported in the daily diary, at Week 6: Analysis of this variable will be the same as described for proportion of subjects with $\geq 30\%$ reduction.

[figure not shown]
In addition, the proportion of subjects with $\geq 70\%$ reduction in the weekly average of daily pain intensity at Week 6 will also be analyzed in the same way as described for the proportion of subjects with $\geq 30\%$ reduction.

Change from baseline in the DSIS at Week 6: Analysis of this variable will be based on an MMRM similar to the analysis of the primary efficacy variable. Weekly average of daily DSIS score at each week will be included in the model as the dependent variable.

Proportion of subjects categorized as improved at Week 6 on the PGIC assessment: This variable will be evaluated using descriptive statistics by treatment group.

Change from baseline in pain intensity on the 11-point NRS, as reported at study visits, at Week 6: Analysis of this variable will be based on an MMRM similar to the analysis of the primary efficacy variable. The change from baseline in NRS at each post-baseline visit (Day 7, Week 3 and Week 6) will be included in the model as the dependent variable.

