12 LIST OF APPENDICES

Appendix A: Analysis Visit Windows for Safety and Efficacy Assessments

Table 12-1 Analysis Visit Windows for Safety and Efficacy Assessments

Assessment	Visit ¹	Target Study Day per the protocol	Analysis Visit Window (in study days)
Safety Assessment			
Hematology	Baseline	1	[Screening visit, Pre-dose Day 1]
Serum Chemistry	Week 3	22	[1*, 32]
	Week 6	43	[33, 57]
	Safety Follow-up Visit	N/A	Nominal
Coagulation	Baseline	N/A	[Screening visit, Pre-dose Day 1]
	Week 6	43	[1*, 57]
	Safety Follow-up Visit	N/A	Nominal
Standard 12-Lead ECG	Baseline	1	[Screening visit, Pre-dose Day 1]
	Day 7	7	[1*, 57]
	Safety Follow-up Visit	N/A	Nominal
Vital Sign	Baseline	1	1
	Day 7	7	[2, 14]
	Week 3	22	[15, 32]
	Week 6	43	[33, 57]
	Safety Follow-up Visit	N/A	Nominal
C-SSRS	Baseline	1	[-1, 1]
	Day 7	7	[2, 14]
	Week 3	22	[15, 32]
	Week 6	43	[33, 57]
	Safety Follow-up Visit	N/A	Nominal

Table 12-1 Analysis Visit Windows for Safety and Efficacy Assessments

Assessment	Visit ¹	Target Study Day per the protocol	Analysis Visit Window (in study days)
Efficacy Assessment			
NRS via daily diary	Baseline	N/A	[-7, -1] ²
DSIS via daily diary	Week 1	N/A	[1*, 7]
	Week 2	N/A	[8, 14]
	Week 3	N/A	[15, 21]
	Week 4	N/A	[22, 28]
	Week 5	N/A	[29, 35]
	Week 6	N/A	[36, 42]
NRS reported at study visits	Baseline	1	Before first dose of study drug
PGIC			
	Day 7	7	[1*, 14]
	Week 3	22	[15, 32]
	Week 6	43	[33, 57]
	Safety Follow-up Visit	N/A	Follow the individual visit window to be mapped to individual visits if measured before / on Day 57 or remain as SFU if otherwise.

1* only include day 1 post-dose measurements.

¹ Visit name for analysis purpose is used to report data in tables and figures.

²Only include 7 day measurements before the randomization day.

Notes:

The analysis visit windows will be applied using the following rules for both scheduled and unscheduled visits:

1. If no numerical measurement is available within a visit window, the measurement will be considered missing for the visit.
2. If there is more than 1 numerical measurement available within the same visit window, use the following rules:
 - a. a. For efficacy assessments: if there are multiple measurements within a visit window,
 - i. The measurement closest to the target day will be used; or
 - ii. If there are multiple measurements within the same distance from the target day, the latest measurement will be used.
 - b. For safety assessments: if there are multiple measurements within a visit window,

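### The SAP does not say which baseline pain score adjusts the visit-NRS secondary endpoint; including both available scores would make the between-group estimate modestly more precise.

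*Protocol*

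**What the plan says.** **Endpoint.** Protocol 7.2 lists "Change from baseline in pain intensity on the 11-point NRS, as reported at study visits, at Week 6" among the secondary endpoints.

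**Data collected.** Protocol Table 3-2 schedules the "11-pt NRS pain score at study visits" at Day -7 and Day 1 as well as after dosing. The same table has the daily diary NRS running from Day -7. Its footnotes give both items the same content: average pain over the last 24 hours on the 11-point scale.

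**Baseline.** SAP 9.1 reserves the run-in average (at least 4 scores from Day -7 to Day -1) for the diary NRS and the DSIS. It then says: "For all other variables baseline will be defined as the most recent nonmissing measurement collected before the initial administration of study drug". SAP 9.3.2.1 assigns visit NRS to that rule, "following the general definition of the baseline and change from baseline in Section 9.1", and Appendix A sets its baseline at target day 1, "Before first dose of study drug".

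**Model.** SAP 9.3.1.2 gives the primary MMRM treatment, sex, diabetes, week and treatment-by-week, plus one baseline pain covariate. SAP 9.3.2.2 bases the visit-NRS analysis on a similar MMRM and specifies only the outcome: "The change from baseline in NRS at each post-baseline visit (Day 7, Week 3 and Week 6) will be included in the model". The baseline covariate is not named.

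**The concern.** If the covariate is the Day 1 visit score, the model adjusts for one day's report and ignores seven pre-dose reports of the same quantity. Between-subject variance that those reports could explain stays in the error term, and chance imbalance between arms in usual pain is only partly removed. If the covariate is instead the diary mean carried over from the primary model, the Day 1 score enters only through the subtraction, with its coefficient fixed at 1, and its day-specific noise goes straight into the outcome.

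What is at stake is the width of one secondary confidence interval. In the text that can be read, visit NRS and DSIS are the only secondary efficacy endpoints with a model-based between-group estimate; the responder and PGIC endpoints are descriptive. Parts of SAP 9.3 are redacted, so this count cannot be confirmed.

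**Working it through.** **The plan's own figures.** No precision or power is stated for visit NRS. For the diary endpoint, Protocol 12.1 and SAP 7.2 assume a difference of 1.25 and an SD of 2.08. At 45 per group the SE is 2.08 × √(2/45) = 0.4385. Power is then Φ(1.25/0.4385 − 1.96) = 81.3% (80.5% with the t distribution), against 81% stated. At 25 and 35 per group the t-based values are 54.9% and 69.8%, against 55% and 70%. These figures reproduce.

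**Inputs for the check.** Only 2.08 comes from the documents, and it is stated for the diary endpoint. The rest are assumptions:
- between-subject SD of baseline pain σb: 1.0 to 1.4 (central 1.2)
- day-to-day SD σw: 0.7 to 1.5 (central 1.0)
- slope b of true Week 6 pain on true baseline pain: 0.7 to 1.0 (central 1)
- correlation of noise between the Day 1 score and the Day -1 diary entry, whose recall periods overlap: 0 to 0.8

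**Model.** Each score is true pain plus daily noise, and T6 = b·T0 + u. The variance of u is set so that the weekly-mean change has SD 2.08: var(u) = 2.08² − (1−b)²σb² − 2σw²/7. Centrally this is 4.3264 − 0 − 0.2857 = 4.0407. With complete data and an unstructured covariance, the Week 6 contrast from the MMRM equals the corresponding ANCOVA, so the SE is proportional to the residual SD of the Week 6 visit score. Central values below assume no noise overlap.

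**Reading 1: the covariate is the Day 1 visit score.**
- Day 1 only: b²σb²σw²/(σb²+σw²) + var(u) + σw² = 1.44/2.44 + 4.0407 + 1 = 5.631, SD 2.373.
- Day 1 plus the 7-day diary mean (8 scores): b²/(1/σb² + 8/σw²) + var(u) + σw² = 1/8.694 + 4.0407 + 1 = 5.156, SD 2.271.
- SE ratio 2.271/2.373 = 0.957 (0.958 with overlap 0.8). The variance ratio is 5.631/5.156 = 1.092, and 9.2% of 90 evaluable subjects is about 8.
- 95% CI half-width at 45 per group: 1.96 × 2.373 × √(2/45) = 0.981, falling to 0.938, a difference of 0.04 points.
- Over the whole grid the SE ratio runs from 0.941 to 0.986, or 0.065 down to 0.012 points of half-width.

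**Reading 2: the diary mean is the sole covariate and change is taken from Day 1.** With b = 1, true baseline pain cancels from the change score. The residual variance is var(u) + 2σw² = 6.041, SD 2.458. The ratio of the two-covariate SE to this is 2.271/2.458 = 0.924, and the grid runs from 0.855 to 0.958.

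**Cross-check with a different parameterisation.** Let r be the reliability of one score (0.5 to 0.9) and ρ the correlation of true pain between baseline and Week 6 (0.4 to 0.8). With r8 = 8r/(1+7r), the reading 1 SE ratio is √[(1 − ρ²·r·r8)/(1 − ρ²r²)].
- At r = 0.7 and ρ = 0.6, r8 = 0.949 and the ratio is √(0.761/0.824) = 0.961. The range is 0.915 to 0.993.
- Simulating the 4-to-9 entry rule of Protocol 8.1 (assumed mean 6, SD 1.8) gives 0.930 to 0.993, central 0.968.
- Reading 2 gives 0.78 to 0.95, central 0.85.

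**Price of an extra slope.** The ratios above treat the slopes as known. Going from three to four roughly normal covariates (sex, diabetes and one pain score, then a second) with 90 subjects inflates the variance of the treatment contrast by (1 + 4/83)/(1 + 3/84) = 1.012, or 0.6% in SE. A fifth term takes it to (1 + 5/82)/(1 + 3/84) = 1.024, or 1.2% in SE. The central gain of about 4% survives this; the low-end gain of 1.4% largely does not.

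**The case against.** The strongest case against is that nothing here is wrong. An MMRM adjusted for a pre-specified baseline on the same instrument is standard, and under randomization the missing covariate introduces no bias. Chance imbalance is already reflected in the interval. The endpoint has no power target or success criterion and largely repeats the primary one, which already averages the diary at both baseline and Week 6. The gain is about 0.04 points, against the 1-point individual minimum important difference in Protocol 9.3.3, and it rests on assumed variances. All of this stands, and it limits the point to an improvement in precision.

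Two stronger readings are tempting, and the documents do not support them.
- A reader might infer that the model adjusts baseline pain only for the Day 1 score. SAP 9.3.2.2 does not say so: a literal carry-over of the primary covariate would be the diary mean. What the text shows is an unnamed covariate. This does not remove the point, because including both scores gave the smaller SE on either reading throughout the grid.
- A reader might also take Protocol 9.3.1 as conceding that a single score is too noisy for this endpoint. Its statement that scores are "averaged over a weekly period to reduce the impact on the analyses of individual high or low pain scores" is made for the primary endpoint and says nothing about covariates for visit NRS.

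**Conclusion.** The point holds as a small, optional improvement together with a real gap in specification. The visit-NRS model has an unnamed baseline pain covariate, and either candidate leaves out information already in hand. If Day 1 is the planned covariate, adding the diary mean lowers the SE of the Week 6 between-group difference by about 1% to 6%, centrally about 4%, before the small price of the extra slope. If the diary mean is the planned sole covariate, the reduction is about 4% to 14% on the same assumptions, centrally about 8%. These sizes depend on the assumed between-subject and day-to-day SDs and slope, and on borrowing 2.08 from the diary endpoint. The direction was the same in every scenario tried. The validity of the visit-NRS analysis and the whole of the primary analysis are unaffected.

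**What to change.** In SAP 9.3.2.2, keep the endpoint and its Day 1 baseline. State that the visit-NRS MMRM includes two baseline pain covariates: the pre-dose Day 1 visit score and the diary baseline mean for Days -7 to -1. Prespecify the fallback for a subject with fewer than 4 run-in diary scores, who has no diary mean under SAP 9.1: use the Day 1 score in its place and add a missing indicator.

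The cost is one model parameter, or two if the indicator is needed. No new data or derivation is required, because the diary mean is already computed for the primary model. SAP section 4 has the plan finalized before database lock, and the sentence should be in place by then. If the sponsor prefers a single covariate, the SAP should still name it.
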